### 3. Study Population:

It is anticipated that this study will begin July, 2014 and will enroll subjects through June 31 of 2019. Follow-up in NICU Graduate Clinic will continue thru June 31, 2020. We are going to enroll 400 infants during that time, male and female all inborn at the University of Kentucky. The population is primarily Caucasian (80%), African American (15%), Asian (3%), and a Hispanic population of about 2%. All races and ethnicities will be included if subjects parent(s) are able to understand English (spoken or written). Pregnant women are considered to also be research subjects in this trial. When the pregnant mother is a

legal adult (18yrs or older) their consent will include their participation as well as their infant. Pregnant women whom are less than 18yrs and greater than 14yrs of age and qualify for enrollment criteria will also be invited to participate in this study. In these cases assent will be obtained from the pregnant mother (who is considered a legal minor), and consent will be obtained from the pregnant mother's legal guardian.

Inclusion criteria

- Neonates with a GA less than 29 6/7weeks (based on last menstrual period and/or early pregnancy ultrasound)
- Consent obtained prior to delivery

Exclusion criteria

- neonates with congenital anomalies such as congenital heart disease
- a prenatal plan to withhold neonatal care
- maternal risks identified by obstetrician, including severe hemorrhage (placenta abruption or placental previa), hypertensive crisis
- if the attending obstetrician or neonatologist decides that infant requires immediate resuscitation for either maternal or newborn well-being
- any prenatal indocin use within 72 hours before birth

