### 2. Study Design:

***The study design of this research project is a randomized, blinded investigation of 4 treatment groups:***

- 1) Control (no intervention);
- 2) DCC alone;
- 3) Prophylactic indomethacin alone;
- 4) Combination of DCC/indomethacin

Infants randomized to block randomization with blocks of size 8 each to randomly assign the subjects into one of the 4 groups. The randomization table will be prepared in advance by the statistician and clinicians will be blinded to this choice prior to the delivery. Investigational Drug Services will provide indomethacin dosing solutions and placebo dosing solutions that are matched in appearance and volume for each study participant. Please note that randomization will occur in all cases, but the attending Neonatologist at delivery and bedside will have authority to define care; if this physician has an objection to the randomization of indomethacin treatment for a specific patient that patient will be excluded from the study. Similar provisions are afforded to the delivering Obstetrician regarding delay of umbilical cord clamp randomization and treatment.

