**4. Subject Recruitment Methods and Privacy: Recruitment:**

[figure not shown]
A total of 400 premature infants born <29 6/7weeks GA will be recruited from the obstetrics admission area and randomized to one of the 4 treatment groups; n=100 each will complete the study (control; DCC alone; Indomethacin alone; DCC + Indomethacin). This facility admits over 800 sick newborn infants/yr and sees a majority of the high-risk obstetrical patients in the Lexington area and beyond. Informed consent will be obtained prior to patient enrollment, by [name] (PI) or another member of the research team experienced at consenting mothers for research studies. There will also be an on-call schedule at night to screen potentially eligible women, enroll them, and attend the births. Women enrolled will be assigned to either immediate or delayed cord clamping groups via a computer generated random number system to assure permuted block randomization. When notified of a subject's impending birth, the research coordinator will open the randomization card, review the protocol with the attending/fellow/or resident obstetrician, and time the cord clamping.

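### The cord allocation is revealed before birth, yet the resuscitation exclusion need not be decided first, so high-risk infants may be excluded more often from the delayed-clamping groups

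*Combined protocol and SAP*

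**What the plan says.** Section 4 (Subject Recruitment Methods and Privacy) fixes when the cord allocation becomes known: "When notified of a subject's impending birth, the research coordinator will open the randomization card, review the protocol with the attending/fellow/or resident obstetrician". The same section says what is allocated: "Women enrolled will be assigned to either immediate or delayed cord clamping groups via a computer generated random number system".

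Section 3 (Study Population) lists among the exclusions: "if the attending obstetrician or neonatologist decides that infant requires immediate resuscitation for either maternal or newborn well-being". It gives no time by which this must be decided and no objective definition.

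Section 6 (Research Procedures) sets clamping at under 10 seconds in the immediate groups and at 45 seconds in the delayed groups. It expects the neonatologist present at the delivery to be unblinded.

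Section 2 (Study Design) says that "clinicians will be blinded to this choice prior to the delivery". It also says that randomisation takes place in every case, but that "if this physician has an objection to the randomization of indomethacin treatment for a specific patient that patient will be excluded from the study". For the cord factor it adds: "Similar provisions are afforded to the delivering Obstetrician regarding delay of umbilical cord clamp randomization and treatment".

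The SAP, under the Aim 1 statistical analyses, adopts intention to treat only where that is judged suitable. It does not say what happens to an infant who is excluded after allocation.

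**The concern.** Both clinicians who may apply the resuscitation exclusion can know the cord arm when they apply it. The criterion is worded neutrally, but it does not bear equally on the two assignments. An infant who needs resuscitation at once can be clamped within 10 seconds as assigned, so nothing prompts an exclusion. The same infant assigned to a 45-second delay presents a direct conflict, and declaring the infant ineligible resolves it.

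If that happens, infants in the worst condition at birth leave the two DCC groups and stay in the two immediate-clamping groups. DCC would then appear to improve survival without severe IVH or PVL even if it did nothing. Covariate adjustment cannot restore infants who are absent from the data, and the loss cannot be repaired later if their outcomes were never collected.

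**Working it through.** **Order of events.** (1) The card is opened at notice of impending birth, with the obstetrician (Section 4). (2) The obstetrician must know the arm by delivery in order to clamp at under 10 or at 45 seconds (Section 6). (3) The newborn's need for resuscitation can be judged finally only around birth. (4) Either the obstetrician or the delivery neonatologist may then exclude (Section 3). No text places step 4 before step 1.

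**Scale.** The plan has no figure to reproduce here: it gives no event rates and no exclusion rates. Every rate below is an assumption.

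Inputs:
- 200 infants per cord arm, from 4 groups of 100 (Section 4).
- No true cord effect.
- Event-free rate 0.80 in ordinary infants.
- A fraction s (0.10 or 0.20) of infants who might be judged to need resuscitation, with event-free rate p (0.60 or 0.50).
- A share e of those infants excluded, which may differ by arm.

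The event-free rate left in an arm is [s(1 − e)p + (1 − s)0.80] / (1 − se).

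Example, s = 0.20, p = 0.50, with 50% excluded in DCC and 25% in immediate clamping:
- DCC: (0.05 + 0.64)/0.90 = 0.7667
- Immediate: (0.075 + 0.64)/0.95 = 0.7526
- Difference: 1.4 points

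Type I error is for the two-sided 5% pooled two-proportion z-test. With SE0 the pooled and SE1 the unpooled standard error and d the difference, P(reject) = Φ((d − 1.96·SE0)/SE1) + Φ((−d − 1.96·SE0)/SE1).

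Example, s = 0.20, p = 0.50, with all such infants excluded in DCC and none in the other arm: 0.80 with n = 160 against 0.74 with n = 200. SE0 = 0.0449 and SE1 = 0.0443, so P(reject) = 0.265.

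False benefit of DCC in percentage points, with type I error in brackets:

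| s, p | 50% v 25% | 75% v 25% | 100% v 0% |
|---|---|---|---|
| 0.10, 0.60 | 0.5 (0.052) | 1.0 (0.056) | 2.0 (0.076) |
| 0.10, 0.50 | 0.7 (0.053) | 1.5 (0.064) | 3.0 (0.109) |
| 0.20, 0.60 | 0.9 (0.055) | 2.0 (0.073) | 4.0 (0.146) |
| 0.20, 0.50 | 1.4 (0.061) | 3.0 (0.101) | 6.0 (0.265) |

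Equal exclusion in both arms gives a difference of 0 and a type I error of 0.05.

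**Second parametrisation, exclusion in the DCC arms only.** Take an overall risk of death, severe IVH or PVL of 20%, with a fraction q excluded whose risk is R. The remaining risk is (0.20 − qR)/(1 − q):
- q = 0.10, R = 0.30: 0.170/0.90 = 18.9%, a false benefit of 1.1 points
- q = 0.15, R = 0.40: 0.140/0.85 = 16.5%, 3.5 points
- q = 0.20, R = 0.40: 0.120/0.80 = 15.0%, 5 points

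**Cost of keeping the infants.** If a share f of DCC infants do not receive the delay, and those infants then gain nothing from the assignment, the intention-to-treat effect is (1 − f) of the full effect. At f = 0.20 it is 0.8, and the sample needed for the same power rises by about 1/0.8² = 1.56. With assumed event-free rates of 75% and 85% and 200 per cord arm, power is 0.71 with full adherence, 0.66 at f = 0.05, 0.61 at f = 0.10 and 0.50 at f = 0.20.

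**The case against.** Several points on the other side are sound.

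*Timing.* Section 3 does not say when any exclusion is judged. A reader might infer that the exclusions are in fact settled after the card is opened; the documents do not say so. An enrolment figure is also missing from the available text and might show the order. What stands is that nothing in the text requires the decision first, and that the newborn part of the resuscitation criterion cannot be finally judged much earlier.

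*Breadth.* A reader might extend the point to the maternal-risk exclusion or to "neonates with congenital anomalies such as congenital heart disease". Many of these are knowable before labour, and there is no evident reason why they would be called differently by arm. A late exclusion that is unrelated to arm does not produce this bias. The resuscitation criterion carries the case.

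*Intention to treat.* No passage states that an infant excluded under Section 3 after allocation leaves the analysis, so a reader who concludes that these infants are certainly dropped goes too far. The qualified SAP wording does not keep them either.

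*Overlap.* An obstetrician unwilling to delay could use the Section 2 objection clause instead. The two routes do overlap, and one definition of the analysis set can close both. It must cover infants declared ineligible as well as those removed on objection.

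*Aim 1B.* The SAP describes Aim 1B both as Group 3 versus Group 4 and as the cord-by-indomethacin interaction. Indomethacin is masked by matched placebo, so cord-driven exclusion should act similarly in Groups 2 and 4 and largely cancel in the interaction.

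*Blinding wording.* The Section 2 sentence on blinding can be read as concealment until the card is opened. Taken literally it conflicts with Section 4, so it needs reconciling. Neither reading removes the problem, because the arm must be known at delivery.

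**Conclusion.** The concern holds as a risk of bias on the cord factor. Followed as written, the plan allows an infant to be excluded for needing resuscitation by clinicians who know the cord arm, under a criterion that conflicts with only one of the two assignments. The likely direction favours DCC, in Aim 1A and in the Group 3 versus Group 4 form of Aim 1B. The interaction form is much less exposed.

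The size is unknown. With moderate imbalance the illustration gives a small distortion, and only near-complete one-sided exclusion brings it to the upper end of the range. The documents do not establish that differential exclusion will occur, and they do not support reading the larger figures as a prediction. The tabulated type I errors are for the comparison of cord arms at 200 each, before exclusions; they do not carry over directly to Group 3 versus Group 4.

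**What to change.** 1. **Sections 3 and 4.** Have the obstetrician and neonatologist confirm eligibility, with a time stamp, before the card is opened. Apply the Section 3 exclusions, above all the resuscitation criterion, only to what is known or decided by then.
2. **SAP, Aim 1 statistical analyses.** Define the primary analysis set as all infants whose card was opened, followed up and analysed as assigned. Record a later need for resuscitation, maternal event or newly found anomaly as a reason for not following the assignment, and report these by arm. Bedside care stays with the clinicians; no clinical rule changes.
3. **Section 2.** Reconcile the statement on blinding before delivery with the card opening in Section 4.

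The administrative cost is protocol and SAP wording plus one time-stamped line on the delivery form. The statistical cost is dilution in proportion to the share of DCC infants who do not receive the delay. It is modest if few miss it and substantial if 10% to 20% do. The plan should state this and check its effect on power once the assumed event rates are given.

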**4. Subject Recruitment Methods and Privacy: Recruitment:**

[figure not shown]
A total of 400 premature infants born <29 6/7weeks GA will be recruited from the obstetrics admission area and randomized to one of the 4 treatment groups; n=100 each will complete the study (control; DCC alone; Indomethacin alone; DCC + Indomethacin). This facility admits over 800 sick newborn infants/yr and sees a majority of the high-risk obstetrical patients in the Lexington area and beyond. Informed consent will be obtained prior to patient enrollment, by [name] (PI) or another member of the research team experienced at consenting mothers for research studies. There will also be an on-call schedule at night to screen potentially eligible women, enroll them, and attend the births. Women enrolled will be assigned to either immediate or delayed cord clamping groups via a computer generated random number system to assure permuted block randomization. When notified of a subject's impending birth, the research coordinator will open the randomization card, review the protocol with the attending/fellow/or resident obstetrician, and time the cord clamping.

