**6. Research Procedures:**

Following enrollment and consent at time of delivery the infant will be placed in one of four groups (per the following algorithm)

For the immediate cord clamping groups the obstetrician will clamp the umbilical cord immediately (<10sec) after birth, per standard procedure. For the delayed cord clamping groups the obstetrician will clamp the cord at 45 sec after delivery and hold the infant in a sterile bag (thermoregulatory bag) 10-15in below the mother's introitus at vaginal delivery or at/below the level of incision if a cesarean section is performed. A stopwatch will identify the time when the infants' buttocks are delivered from the vagina or the

uterus (or head if breech); time elapsed will be counted in 10sec intervals for the OB by the investigator. Infants in the DCC group will be placed into a sterile bag to minimize heat loss at the sterile field by the delivery OB. Per standard NICU clinical protocol, infants in the ICC groups will be placed in the thermoregulatory bag once they are placed on the neonatal warming bed.

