**Aim 1 Statistical analyses: [all analyses performed as 'intention to treat' where appropriate]:** To investigate the primary hypothesis in Aim 1A (treatment-related outcome differences with respect to the primary endpoint fraction of cases surviving without severe IVH, grade 3 or 4) we will use head ultrasound data from day of life 0-30, and use two distinct approaches. First, based on the qualitative data used to compute the sample size, we will employ a bivariate analysis to identify the significant covariates, followed by a multiple logistic regression analysis to test for differences between the four groups in the presence of significant covariates. Secondly, we will develop severe IVH or PVL data and employ survival analysis statistics (log rank Mantel-Cox test). If the assumptions are validated, we will use the Cox proportional hazard model for this survival data. In addition we will compare head MRI results (measured at the single time point of 38wks adjusted gestational age using a multiple regression model that will incorporate significant covariates. Aim 1B is concerned with comparison of Groups 3 and 4 only (e.g. Indomethacin vs. Indo-DCC) and the procedures developed for the 4 group analysis are also applicable here. For Aim 1C we correlate later performance with the short term brain imaging results in the framework of a multiple regression model where the 4 groups will be used as predictors and will be compared. In all settings we will also perform separate analyses of IVH alone, and PVL alone.

Aim 1 also involves comparisons of nominal/ordinal and continuous variables associated with neurodevelopment and toxicity where single or repeated measures on the response are available. Approaches similar to the one described above will be taken where we first build a statistically valid model that controls for all influential covariates and test the relevant hypotheses in the context of the model. Aim 1B corresponds to the testing of the interaction effect between the ICC/DCC effect and the use of prophylactic indomethacin. Other hypotheses correspond to the main effects. We will also compare the variables that reflect renal function/status (as assessments of potential indomethacin toxicities, other specific comorbidities and hospital stay related variables across the 4 groups.

**Aim 2: Investigate mechanistic effects of prophylactic indomethacin, DCC, and their combination in infants less than 28wks gestational age.**

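### The unit of assignment is contradictory (women in one place, infants in others), siblings can enter, and no analysis allows for correlation between them

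*Combined protocol and SAP*

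**What the plan says.** **Unit of assignment.** The protocol gives two answers.
- Mother: Section 4 (Subject Recruitment Methods) says "Women enrolled will be assigned to either immediate or delayed cord clamping groups via a computer generated random number system".
- Infant: Section 2 (Study Design) says "Infants randomized to block randomization with blocks of size 8 each to randomly assign the subjects into one of the 4 groups". The first sentence of Section 4 also has 400 premature infants randomised to the four groups, and Section 6 (Research Procedures) says that "the infant will be placed in one of four groups".
- Study drug: Section 2 describes active and placebo solutions "matched in appearance and volume for each study participant". This suggests assignment per infant but does not settle it, because Section 3 counts pregnant women as research subjects too.

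**Siblings.** Eligibility in Section 3 is defined per neonate. None of the listed criteria mentions twins or higher multiples, and nothing limits enrolment to one infant per mother. No rule says how siblings are assigned to either factor.

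**Counting.** The sample size is in infants: "We are going to enroll 400 infants during that time" (Section 3) and "n=100 each will complete the study" (Section 4).

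**Analysis.** For the primary outcome, the SAP names a "multiple logistic regression analysis to test for differences between the four groups", then a log-rank test and, if its assumptions hold, a Cox model; MRI and follow-up outcomes go to multiple regression. The Aim 3 text says that power was based on chi-square tests of proportions. None of these comes with a cluster term, a robust variance or a design effect. The mixed models under Aim 2 are for repeated measurements over time.

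**The concern.** The log-rank and chi-square tests, and logistic, Cox and linear models in their standard form, assume independent observations. Siblings share a mother and a pregnancy, and so nearly always a gestational age. Under the women-based sentence in Section 4 they also share the cord-clamping arm.

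If siblings are in the same arm and their outcomes are positively correlated, they carry less information than two unrelated infants. The naive standard error is then too small and the test rejects too often. If they are in opposite arms, their shared background cancels in the comparison, the naive standard error is too large, and power is lost. With clamping assigned by mother and drug by infant, the two factors of one trial could be in error in opposite directions. Aim 1B, which the SAP links to the interaction of these factors, would depend on both.

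**Working it through.** **1. The plan's own figure.** 4 groups x 100 = 400, which agrees with the stated total. Nothing further can be rebuilt, because event rates, effect size, power and the alpha of the main test are not in the documents. No design effect is mentioned.

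**2. Inputs assumed.** The documents give neither of these, so both are shown as ranges.
- f, the share of infants who belong to an enrolled twin pair with both twins analysed: 0.15 to 0.30.
- rho, the within-pair correlation of the outcome left after covariates: 0.2 to 0.6.
- Two-sided alpha of 0.05 (the SAP states 0.05 only for entry of variables into models).

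**3. Siblings in the same arm.**
- Design effect DE = 1 + f x rho. Low: 1 + 0.15 x 0.2 = 1.03. High: 1 + 0.30 x 0.6 = 1.18.
- True SE / naive SE = sqrt(DE): 1.015 to 1.086. The true SE is 1.5% to 8.6% larger than the naive SE. Equivalently, the naive SE is understated by 1 - 1/sqrt(DE), which is 1.5% to 7.9%.
- Two-group type I error = 2 x (1 - Phi(1.96/sqrt(DE))). Low: 1.96/1.015 = 1.931, giving 5.4% (5.35%). High: 1.96/1.086 = 1.804, giving 7.1% (7.12%).
- Effective sample size = 400/DE: 388 to 339.

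A simulation of 200 against 200 infants, with an assumed outcome rate of 0.8 and 20,000 runs, supports the formula. It gave 4.9% with no twins and 6.3% at f = 0.3, rho = 0.3, where the formula gives 6.05%.

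**4. Siblings split between the compared arms.**
- If every pair is split, DE = 1 - f x rho: 0.97 to 0.82.
- True SE / naive SE: 0.985 to 0.906, so the naive SE is too large.
- Type I error: 1.96/0.985 = 1.990 gives 4.7%; 1.96/0.906 = 2.164 gives 3.0%.

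**5. Mixed case.** If a share c of pairs is in the same arm and 1 - c is split, DE = 1 + f x rho x (2c - 1). Fully independent assignment per infant gives c near one half and DE near 1. The size and direction of the error therefore depend on the sibling rule, which the plan does not give.

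**6. Interaction (Aim 1B).** Code each factor as +1 or -1. The interaction term is the product of the two codes. For siblings who share the cord arm and are split on drug, their two interaction codes have opposite signs. That contrast then behaves as in step 4, while the clamping main effect behaves as in step 3.

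**The case against.** - **The women-based sentence may be loose wording.** The card is opened before birth, through the mother, and three other places name the infant. A figure in Section 4 is not shown, and Section 6 points to an algorithm that is absent from the extracted text; either might settle the unit. This stands: a reader might infer that clamping is definitely assigned by mother, and the documents do not establish that. It does not repair the analysis, because siblings may be enrolled under either reading and no sibling rule or clustering is stated.
- **Independence is never asserted.** This also stands. It is inferred from the methods named and the absence of any adjustment. A short SAP may leave the variance estimator open, but followed as written these methods make no allowance for siblings.
- **Errors need not be wrong whenever siblings are enrolled.** Correct. If residual correlation is nil, so is the error. Adjusting for shared covariates such as gestational age could absorb part of it, which weakens the upper end of the range more than the lower.
- **The size is all assumption.** Correct, and the low end (5.4% against 5%) is negligible. A reader might also take 5.4-7.1% as the error rate of the four-group primary test. It is not: it describes a two-group comparison with siblings in the same arm. If drug is assigned per infant, siblings can share a cord arm yet sit in different groups.

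**Conclusion.** The point holds in conditional form. The unit of assignment is stated inconsistently, siblings are not excluded, no rule covers their assignment, and neither the analyses nor the power basis allows for their correlation. If siblings are enrolled and their outcomes are correlated, the planned standard errors are not valid, and the direction of the error depends on whether siblings share or differ on the factor tested.

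Under the assumptions in the working, the effect is modest: two-group type I error of 5.4-7.1% when siblings share the arm, and 4.7-3.0% when every pair is split. The documents cannot narrow these ranges. The trial is not invalid on this account, but the plan should be corrected, since a suitable analysis is standard and cheap.

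**What to change.** 1. Reconcile Sections 2, 4 and 6 on one stated unit of assignment for each factor. Say how siblings are assigned to cord clamping and how they are assigned to study drug.
2. Record a mother identifier for each infant. Mothers are already consented subjects, but the data collection instrument is not shown, so whether the link is already captured cannot be told.
3. Cluster the Aim 1 and Aim 2 models by mother: GEE or cluster-robust errors for logistic and linear models; Cox with robust variance or a frailty term in place of the plain log-rank test; and a mother random effect, in addition to the infant-level one, in the repeated-measures mixed models. Where most mothers contribute one infant, GEE or robust errors are likely to be more stable for binary outcomes than a random effect.
4. State beside the chi-square power basis the expected share of multiples and the design effect that it implies.

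The cost is SAP and protocol wording plus one data field, with no extra visits. Intervals become slightly wider for factors that siblings share and narrower for factors on which they are split. If no siblings are enrolled, the results are essentially unchanged.
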